1.0 STUDY OBJECTIVES

This project will test the use of an eHealth intervention called C-CHESS, to modify health behaviors and improve health outcomes in older adults with comorbid chronic diseases and health conditions.

Aim 1 Refine C-CHESS, using feedback from patients and primary care clinicians.

Aim 2 Conduct a randomized clinical trial to test 4 hypotheses:

1. *Primary outcomes:* Patients assigned to TAU+C-CHESS will have better quality of life and less primary care use (fewer visits) than those assigned to TAU+Internet.
2. *Secondary outcomes:* Patients assigned to TAU+C-CHESS will have improved composite scores; improved individual condition outcomes (mm Hg for hypertension, mg/dL for hyperlipidemia (LDL), HbA1c for diabetes, and pain for arthritis); and fewer symptoms from a list than patients assigned to TAU+Internet.
3. *Mediators:* Patients assigned to TAU+C-CHESS will have, compared with patients assigned to TAU+Internet, greater adherence to medications and appointments as well as improved competence,

relatedness, and autonomy.

4. *Moderators:* Improvements in primary outcomes for TAU+C-CHESS vs. TAU+Internet will be greater for women than men, those ≥ 75 vs. 65 to 74, and those with 3-5 chronic conditions vs. 6+.

Aim 3 Analyze data from the RCT and publish results.

Exploratory questions:

- Does C-CHESS reach a large proportion of targeted patients, get a large proportion of targeted clinicians to use C-CHESS, get a large proportion of patients to regularly use C-CHESS, and maintain that performance over time)?
- Does the use of specific C-CHESS services affect outcomes?
- Does the use of C-CHESS affect other health service use?

Primary Aim

Patients assigned to TAU+C-CHESS will have better quality of life and fewer primary care visits than those assigned to TAU+Internet.

C-CHESS will contain the Clinician Report to make it easier for PCPs to respond to important patient changes, pilot data suggested that primary care visits could be reduced. Reducing the number of primary care visits will both lessen provider burden and ultimately reduce healthcare costs.

Secondary Aim

Patients assigned to TAU+C-CHESS will have improved composite scores; improved individual condition outcomes (mm Hg for hypertension, mg/dL for hyperlipidemia (LDL), HbA1c for diabetes, and pain for arthritis); and fewer symptoms from a list than patients assigned to TAU+Internet.

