The research team will always have a member available during standard operating hours for participants to contact with questions or issues. If a patient declines to participate, a research team member will determine reasons for non-participation so we can examine how patients who opt out differ from those who choose to participate.

The consent process will inform potential subjects of:

- (1) the nature and purpose of the study
- (2) the types of data that will be collected quarterly from the EHR (by the CRDS) and, for participants in the experimental group, from C-CHESS
 - Systolic and diastolic BP
 - Weight
 - BMI
 - HDL/LDL
 - HbA1C
 - pain score
 - health care utilization: hospitalizations (admission and discharge), number of ER visits, urgent care visits, PC visits, specialty care visits, long-term care visits, and rehab visits
 - osteoporosis
 - cancer
- (3) for participants in the experimental group, the types of data that will be shared with their primary care physician (a graph that charts weekly scores related to the quality of your sleeping, nutrition, physical activity, memory, falls, moods, balance, pain, medication adherence and quality time spent with others.)
- (4) study risks and measures taken to mitigate

(5) their right to leave the study at any time

(6) the timeline of the study

Consent will be documented by obtaining a signed, IRB-approved consent forms from participants. Signed forms and other study data will be stored in a locked cabinet at the Center for Health Enhancement Systems Studies at the UW. After receipt of the signed consent forms, patients who need them will be issued their computer by research staff. Research staff will train patients on Internet safety and security and how to use the intervention. Research staff will help participants assigned to the experimental group choose a unique login name and password for C-CHESS. Subjects will be asked to use the intervention weekly.

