Mediation. We will test 4 potential mediators of the intervention's effect on the primary and secondary outcomes. We will also test whether the condition-specific and composite secondary outcomes mediate the intervention's effect on the primary outcomes. Mediation will be tested by individually testing the 2 paths in the indirect effect and will conclude statistical significance only when the null hypothesis of no effect is rejected for both paths in the mediational pathway. To limit the number of analyses, we will use Bolt's approach⁹⁴ of first using a screening approach that examines only mediational models with outcomes and potential mediators significantly affected by the intervention. We will then use separate univariate models to determine which mediate the intervention effect on given outcomes. If 2 or 3 mediators are found, we will simultaneously enter all the significant mediators into the same model. If 4 mediators are found, we will enter the 'strongest' mediator first and then test whether adding remaining mediators shows significant mediational effects.

Moderation. A moderation model holds that the strength of the relation between intervention and outcomes is a function of the level of other variables and tries to explain under what conditions the treatment model functions. We will test whether gender, age (65-74 vs ≥ 75), and number of chronic conditions (3, 4, or 5) moderate the effect of the intervention on outcomes. Also, when standardized composites are used as the dependent variable, type of chronic condition will be used as a moderator to determine if the composite varies meaningfully by condition. Participants will list changes in chronic conditions at 6 and 12 months.

Moderated mediation. Although both constructs of mediation and moderation are of interest in our research, the process is more complex than just these factors. For example, a variable (e.g., relatedness) may act as a stronger mediator for 1 subgroup (e.g., women) than another (e.g., men).

Qualitative analyses. Through 3 interviews we will gather qualitative data from clinic staff to provide additional insights into their use of the CR.

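### The mediation rule ignores direction, so appointment adherence could be reported as a mediator of fewer primary care visits when its indirect effect is toward more visits

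*Combined protocol and SAP*

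**What the plan says.** Section 1.0 sets two expectations that meet in one analysis. The Primary Aim is that "Patients assigned to TAU+C-CHESS will have better quality of life and fewer primary care visits than those assigned to TAU+Internet". Hypothesis 3 under Aim 2, on mediators, expects "greater adherence to medications and appointments as well as improved competence", along with gains in relatedness and autonomy. The Background section describes a C-CHESS service that reminds patients of upcoming appointments, so a rise in appointment adherence is a planned effect.

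The Mediation paragraph of Section 6.0 then states "We will test 4 potential mediators of the intervention's effect on the primary and secondary outcomes". A screen comes first and "examines only mediational models with outcomes and potential mediators significantly affected by the intervention". For the pairs that pass, the plan "will conclude statistical significance only when the null hypothesis of no effect is rejected for both paths in the mediational pathway". Variables that meet this rule are described as mediating the intervention's effect on that outcome, and they go forward to joint models. The plan sets no condition on the sign of either path. It does not ask for an estimate or interval of the indirect effect, and it does not exempt the pairing of appointment adherence with visits.

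**The concern.** Hypothesis 1 wants visits to go down and Hypothesis 3 wants appointments to be kept. With scheduling held fixed, each additional primary care appointment kept adds one to the visit count. If that overlap dominates, the path from adherence to visits (b) is positive. Adherence goes up under C-CHESS, so the indirect effect a × b is also positive, that is, toward more visits, while the total effect is toward fewer.

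That pattern is suppression (inconsistent mediation): visits fall despite the mediator. The screen and the two-path rule cannot tell it from true mediation, because both look only at whether effects differ from zero. A variable working against the reduction could therefore be published as an explanation of it, for a primary outcome. The exposure is greatest when both of the trial's hypotheses come true, because only then does the pair pass the screen.

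**Working it through.** **The plan's own figures.** Section 8.0 gives 100 per arm for d = 0.40, 80% power and two-sided 5%. Check: n = 2 × (1.96 + 0.8416)² / 0.40² = 2 × 7.849 / 0.16 = 98.1, so 99 per arm, in line with the stated 100. Its analysed total is 264 (132 per arm), and 264 / (1 − 0.20) = 330, as stated. The plan gives no operating figure for the mediation rule, so that has to be worked out.

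**Inputs.** From the documents: N = 264, 1:1 allocation, d = 0.40 on the outcome, two-sided 5%, and the screen and two-path rule of Section 6.0. Assumed: adherence also moves by 0.4 SD (a = +0.4), and b takes a range of values, because the documents give none.

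**Model.** With T as arm, adherence is M = 0.4T + error. Visits, on a standardised scale, are Y = c′T + bM + error, with residual SD √(1 − b²). The total effect is fixed at c′ + 0.4b = −0.40, so the direct effect is c′ = −0.40 − 0.4b and the indirect effect is 0.4b.

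**Screen.** Each arm comparison has expected z = 0.4 × √(132/2) = 3.25, so its power is Φ(3.25 − 1.96) = 0.90. Both significant: about 0.90² = 0.81. Simulation gives 0.80 to 0.82.

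**Second path.** Expected z = b√264 / √(1 − b²), with √264 = 16.25, and power = Φ(z − 1.96). Multiplying by a screen pass rate of 0.80 approximates how often the rule declares mediation. The simulated column applies the full rule (4,000 trials per setting; a range shows repeat runs).

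| b | Indirect | Direct | z, path b | Power, path b | × 0.80 | Simulated: declared | Of those, opposing sign |
|---|---|---|---|---|---|---|---|
| −0.3 | −0.12 | −0.28 | | | | 82% | 0% |
| 0 | 0 | −0.40 | | | | 4% | 56% |
| 0.1 | +0.04 | −0.44 | 1.63 | 0.37 | 0.30 | 28–30% | at least 99.9% |
| 0.2 | +0.08 | −0.48 | 3.32 | 0.91 | 0.73 | 72–73% | 100% |
| 0.3 | +0.12 | −0.52 | 5.11 | >0.99 | 0.80 | 79–80% | 100% |

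At b = 0.3, adjusting for the supposed mediator makes the treatment effect larger (−0.52 against −0.40). The share mediated would be 0.12 / −0.40 = −30%.

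**With a sign condition.** If a × b must also match the sign of the total effect, declarations fall to about 0% for b > 0. At b = −0.3 they stay at 82%, so the condition costs nothing when mediation is real.

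**A count version.** Assume mean scheduled visits of 5.0 (control) and 3.6 (C-CHESS), with kept shares of 0.80 and 0.88. Expected visits are 5.0 × 0.80 = 4.0 and 3.6 × 0.88 = 3.17. A Poisson analysis declared mediation in 85% of simulated trials, every one with the opposing sign. The average log-scale effects in those trials were indirect +0.11, direct −0.35 and total −0.25. Here b is positive by construction, because all visits are scheduled ones.

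**The case against.** The strongest reply is that the sign of b is an assumption. Visits also include unscheduled ones, and keeping planned appointments may prevent some of these. Take 132 per arm, a mean of 2 or 4 scheduled visits, 25% fewer scheduled on C-CHESS, and kept shares of 82% against 92%. With scheduled visits only, at least 80% of trials passing the screen are declared mediated, all with the wrong sign, but only about 24% to 65% of trials pass. Now add overdispersion and an equal mean of unscheduled visits that falls with adherence. Declarations drop to 10–16% of screened trials, and at a mean of 4 the sign largely reverses; at a mean of 2, 95% of declared cases still point to more visits. This stands: the error is possible, not certain.

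Second, the overlap may be diluted. Hypothesis 3 does not say primary care appointments. If medication and appointment adherence are separate, it names five constructs; Section 6.0 counts four, so adherence may be one pooled mediator. This also stands, but pooling weakens b without checking its sign.

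Third, testing both paths jointly is a standard method, and an analyst could notice a positive b beside a falling outcome. That is true, but the rule as written does not require anyone to look.

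A reader might go further and infer that any adherence measure would simply be the visit count, since the data collected from the health record are listed as "number of ER visits, urgent care visits, PC visits, specialty care visits, long-term care visits, and rehab visits" with no scheduled or missed appointments. The documents do not support that. Section 6.0 announces a list of instruments that is not in the text available here, and the surveys also collect health care utilization.

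**Conclusion.** The point holds as a gap in the decision rule. For appointment adherence and primary care visits, the plan could report suppression as mediation, because neither the screen nor the two-path rule considers direction. Under the assumptions above (N = 264, adherence up 0.4 SD, visits down 0.4 SD), this happens in about 28%, 73% and 79% of trials for b = 0.1, 0.2 and 0.3. If b is negative, a declared mediator has the right sign and there is no such error.

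It would be tempting to conclude that the plan will credit adherence with the fall in visits. The documents do not support that: it needs a significant rise in adherence, a significant fall in visits and a positive b, and the last is not given. Nor do they show that success on Hypothesis 3 must cancel Hypothesis 1. The overlap concerns the visits outcome only, not quality of life. No primary estimate, test or sample size changes; what is at risk is the mechanism reported for a primary outcome.

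**What to change.** In the Mediation paragraph of Section 6.0, add for every mediator-outcome pair:

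- Report the indirect effect with its sign and a confidence interval, beside the direct and total effects on the same model scale.
- Claim mediation of the treatment effect only when both paths are significant and the indirect effect has the same sign as the total effect.
- When the signs differ, report the result as suppression (inconsistent mediation), and do not carry that variable into the joint models as a mediator.

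The cost is a few sentences and one interval per pair. In the check above, no power was lost when mediation was real (82% with and without the condition at b = −0.3).

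The pair need not be dropped: that would close off a legitimate mechanism if b is negative, and the sign condition already handles the positive case. Adding scheduled and missed appointments to the record extract, or splitting the visit count, is not needed for this fix. Those changes would also touch the consent list in a study that, by its own dates, began recruiting in January 2018 and already carries text about October 2019.

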2.0 SELECTION OF SUBJECTS

Patient Recruitment: We will recruit 330 patients age ≥ 65 .

Patients are eligible for the study if they:

- 1) are ≥ 65 years old
- 2) have been treated in the clinic for at least the previous 18 months with no plans to leave during the study period

- 3) have ≥ 3 of the following chronic conditions:
 - Hypertension
 - Hyperlipidemia
 - Diabetes
 - Arthritis
 - BMI ≥ 30
 - Chronic Kidney disease
 - Chronic pain
 - COPD
 - Congestive heart failure
 - Arrhythmia/atrial fibrillation
- 4) report no current psychotic disorder that would prevent participation
- 5) have no acute medical problem requiring immediate hospitalization
- 6) do not have a visual or motor impairment that prevents them from using a computer
- 7) be able to read and sign the consent form in English
- 8) have no known terminal illness;
- 9) be willing to share health-related study data and
 - Systolic and diastolic BP
 - Weight
 - BMI
 - HDL/LDL
 - HbA1C
 - pain score
 - health care utilization: hospitalizations (admission and discharge), number of ER visits, urgent care visits, PC visits, specialty care visits, long-term care visits, and rehab visits
- 10) allow researchers to share information with their primary care physician

We will document and describe eligible people who choose not to participate.

Clinician Recruitment: 15 providers (salaried, credentialed staff) from 5 different clinic sites will be identified and recruited to complete 3 qualitative interviews each over the course of the study. Site staff will be identified by the clinic and contacted by the UW study coordinator. Details of the study and their participation will be explained and if they agree informed consent will be collected. Staff are eligible for the study if they:

- Allow monitoring of their C-CHESS usage
- Are willing to participate in 3 interviews to share information about technology use at their clinic and feedback related to C-CHESS.
- Have a patient participating in the intervention arm of this study

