3.0 REGISTRATION PROCEDURES

Patient Recruitment

In January of 2018, research staff will begin recruiting. The trial will involve 330 patients age 65 and older, randomized into two groups:

1. Patients in the experimental group will receive treatment as usual TAU + laptop + Internet access + C-CHESS
2. Patients in the control group will receive TAU + laptop + Internet access

Patient recruitment will be conducted in primary care clinics within the University of Wisconsin's Department of Family Medicine and General Internal Medicine, as well the Medical University of South Carolina.

School of Medicine and Public Health/MUSC employees will identify from clinic records patients who meet inclusion criteria.

The UW Clinical Research Data Service (CRDS) will extract the following data to determine patient eligibility per the eligibility criteria above. The data will be sent to the UW Office of Clinical Trials via REDCap or other secure method.

- First and last name
- Address
- Birth date
- Age
- UW Clinic Location
- Primary Care Doctor
- Has ≥ 3 of the following chronic conditions:
 - Hypertension
 - Hyperlipidemia
 - Diabetes
 - Arthritis
 - BMI ≥ 30
 - Chronic Kidney disease
 - Chronic pain
 - COPD
 - Congestive heart failure
 - Arrhythmia/atrial fibrillation
- # of chronic conditions
- Don't need an interpreter
- # of primary care visits in the last 18 months

Potential UW Health participants will either receive an opt-in letter from the UW Office of Clinical Trials or be recruited in-person at a scheduled clinic appointment. In the latter case, clinic staff or the Office of Clinical Trials will alert research staff when a potential participant has an upcoming clinic appointment. Staff will be available at the clinic on the specified date/time to conduct the enrollment visit if the patient agrees to speak with them.

Potential MUSC participants will receive an opt-in letter or MyChart message sent by the MUSC Biomedical Information Specialist. The message will describe the study and have a postage paid return letter inviting further contact from the UW study team.

Only MUSC, the UW Office of Clinical Trials, or SMPH Family Medicine staff will receive the list of potential subjects, process the mailings or MyChart messages, or identify upcoming clinic appointments.

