UW study staff will call potential participants who opt-in to provide a detailed study overview including the benefits and potential risks of participation. If the patient is interested in participating, they will be asked questions to determine final eligibility: 1) do they have any acute medical problem requiring immediate inpatient treatment, 2) are they willing to allow their health care provider to supply lab data to the study team, or 3) are they willing to allow the study team to share high level information (graph that charts weekly scores related to the quality of your sleeping, nutrition, physical activity, memory, falls, moods, balance, pain, medication adherence and quality time spent with others, 4) do they have any plans to change health care providers in the next 18 months.

Patients who verbally confirm they want to be in the study and meet the screening criteria will be mailed the baseline survey and will receive a home visit where written consent will be obtained, the completed baseline collected, randomization determined, equipment set up, and training delivered. The baseline survey is expected to take 20-30 minutes to complete and will assess demographics, quality of life, symptom management, pain, medication adherence, and health care utilization.

Patients who consent to participate in-person at a clinic appointment will provide signed consent, be given the baseline survey, and a home visit will be scheduled to complete the activities described above.

Minority Recruitment Advisors

In addition to the general recruitment procedures described above, beginning in October 2019 three individuals active in the black community in Madison, WI will serve as advisors to the research team. They will provide feedback on recruitment materials, recruitment process, and ElderTree content and design which will inform future projects.

Patient Consent

Patients must agree to allow monitoring of their C-CHESS use and agree to allow their clinic to supply the study team with health care utilization and EHR related data, specifically lab scores for systolic and diastolic BP, weight, BMI, HDL/LDL, HbA1C, and pain. (as applicable to the patient), and diagnoses of anxiety, depression, osteoporosis, and cancer. The patient will be given the right not to share specific information and will retain the right to revoke their permission at any point.

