Participants who do not already own a computer will be receiving a laptop as part of the study. The laptop has an administration interface that allows our technical team to access devices remotely if a participant calls tech support or reports a problem. If a participant loses their laptop or installs something that is causing problems, we have the ability to remotely wipe the device, lock it down, restore the operating system and/or run a security check. We can also do security updates remotely to make sure patches are up to date on each laptop and security software has not been disabled by the user.

Patient Randomization: Once informed consent and baseline measures have been obtained from patients, they will be randomized to either the experimental (TAU + C-CHESS) or control (TAU + Internet) group, stratified on gender, clinic site, and number of chronic conditions (3-5 vs. 6+). Patients who are in the experimental group will be further randomized into two groups, one will be asked to identify a health outcome to track and share with their physician using the Clinician Report and the other group will not.

When baseline assessment and consent are complete, the researcher will enter the participant number and randomization data into a randomization spreadsheet. The interviewing researcher, once informed of group assignment, will provide setup and training.

The research staff will train participants to use C-CHESS and customize it (e.g. by health condition) during a home visit. Participants will be asked to check in regularly, initially at a daily rate with frequency of at least weekly over the course of the study.

Patient Qualitative: Data will be gathered via an interview at 3 times from 6 patients at each of the 5 clinics (N=30). Each interview is expected to take 30-60 minutes and will take place either in-person at a place of the subjects choosing or via phone.

Recruitment: Participants will be identified through a consent form opt-in question and demographics as reported on the baseline survey. We will seek a mix of genders and number of chronic conditions. We will also look at C-CHESS use data to find a mix of users and non-users. We will contact potential participants by messaging them through the C-CHESS application or phoning them.

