7.0 STUDY PARAMETERS

Patients will be randomized on a 1:1 ratio to TAU + internet or TAU+C-CHESS. Subjects will be stratified by gender, number of conditions and study site. It is anticipated that up to 330 patient subjects will be recruited at the participating clinics. Staff subjects will have access to C-CHESS for the duration of the study. Patient will have access to C-CHESS for 12 months.

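### Age moderation is framed and tested as 65-74 versus 75 or over; if the C-CHESS effect changes steadily with age, testing age in years would recover about 25-44% of the information at almost no cost

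*Combined protocol and SAP*

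**What the plan says.** Section 6.0 (Moderation) lists the moderators and gives age in two categories: "We will test whether gender, age (65-74 vs" 75 or over). Hypothesis 4 in section 1.0 opens with "Improvements in primary outcomes for TAU+C-CHESS vs. TAU+Internet will be greater for women than men" and continues with the age contrast "those ≥ 75 vs. 65 to 74". Hypothesis and analysis therefore agree on the two groups.

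On the age data, section 3.0 (Patient Recruitment) says that the UW data service "will extract the following data to determine patient eligibility", and its field list includes both birth date and age. No matching list is given for MUSC. The baseline survey "will assess demographics, quality of life" and other items, without saying how age is recorded. The age criterion in section 2.0 is that patients "are ≥ 65 years old", with no upper limit.

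Randomisation is "stratified on gender, clinic site, and number of chronic conditions (3-5 vs. 6" or more). Age is not among these factors, and section 7.0 does not add it.

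Section 8.0 has a power statement for mediation and moderation. It says that a total of 220 patients gives power above .80 for a group difference of .4 SD in a parameter, and that the 264 patients of the primary analysis are therefore enough.

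**The concern.** The two-group test treats a patient of 65 and one of 74 as alike, and one of 74 and one of 75 as different. If the benefit of C-CHESS rises or falls steadily with age, a test on age in years uses the whole gradient, while the cut uses only the difference between two averages. The null hypothesis, that age does not modify the effect, is the same in both.

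The design does not require the cut, since age is not a stratum, and the documents give no reason for choosing 75. What is at stake is precision for an arm-by-age interaction, which is harder to detect than a main effect and for which no patients are added beyond the 264.

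**Working it through.** **Inputs from the documents.** Two-sided alpha .05, power .80, d = .40, 264 patients analysed, and 220 for moderation (section 8.0); 1:1 allocation (section 7.0: "Patients will be randomized on a 1:1 ratio to TAU + internet or TAU+C-CHESS"); minimum age 65 (section 2.0).

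**Assumptions, not in the documents.** The age distribution, the share aged 75 or over, and the shape of the age effect. Normal approximation throughout, on a standardised outcome with unit SD and no gain from baseline adjustment. The visit count is treated on the same d scale that section 8.0 uses.

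**Step 1: the plan's own figures.** Two means at d = .40 need 99 per arm, 198 in total, against 200 stated. 264 / (1 − .20) = 330, as stated. For moderation, 220 patients in two equal groups give .4 × √(110/2) = 2.97, and Φ(2.97 − 1.96) = .84. This agrees with a power above .80, but as a simple difference between two groups. The structural model behind the stated method is not given, so that calculation cannot be repeated directly.

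**Step 2: information kept by the cut.** If moderation is linear in age, the efficiency of the two-group test relative to age in years is r², the squared correlation of age with the indicator for 75 or over.

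| Assumed ages | Share 75+ | r² | Loss |
|---|---|---|---|
| Uniform 65-85 | 50% | .75 | 25% |
| Uniform 65-90 | 60% | .72 | 28% |
| 65 + exponential, mean 9, capped at 100 | 32% | .69 | 31% |
| Normal (73, SD 6), truncated to 65-95 | 41% | .67 | 33% |
| 65 + exponential, mean 7, no cap | 24% | .64 | 36% |
| 65 + exponential, mean 9, no cap | 33% | .61 | 39% |
| Normal (70, SD 5), truncated to 65-95 | 19% | .565 | 44% |

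For the uncapped exponential with mean m, p = exp(−10/m) and r² = 100p / [m²(1 − p)]. With m = 9, p = .329 and r² = 32.9 / (81 × .671) = .61. An upper age cap matters: the same distribution gives .69 when capped.

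**Step 3: effect on power.** Power .80 at two-sided .05 needs a noncentrality of 2.80. The cut multiplies this by √r²:

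- r² = .75: 2.80 × .866 = 2.43, power Φ(2.43 − 1.96) = .68
- r² = .61: 2.80 × .778 = 2.18, power .59
- r² = .565: 2.80 × .752 = 2.11, power .56

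In patients, 264 × .75 = 198 and 264 × .565 = 149.

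**Step 4: power in this trial.** Take a .4 SD difference of differences with 35% of the 264 aged 75 or over (92.4 and 171.6 patients). SE = √(4/92.4 + 4/171.6) = .258, and .4/.258 = 1.55.

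- With the cut: Φ(1.55 − 1.96) = .34. At a 50:50 split it is .37, and with 25% aged 75 or over it is .29.
- Age in years, linear truth, r² = .68: 1.55/√.68 = 1.88, power .47.
- Age in years, true step at 75, r² = .68: 1.55 × √.68 = 1.28, power .25.

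For 80% power on a .4 SD interaction at a 50:50 split, the total would be 16 × 2.80² / .4² ≈ 785.

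**The case against.** The strongest defence is that the plan tests exactly what it hypothesises. A reader might infer that the hypothesis is a gradient and that the analysis departs from it. The documents do not support that, because hypothesis 4 is itself a contrast of 75 or over with 65 to 74. Changing the test also means changing the hypothesis, and the two edits must be made together. This stands.

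The second defence is that neither choice wins in every case. The same r² applies in both directions: if the effect steps at 75, the linear test loses the share that the cut loses under a gradient (.34 falls to about .25 in step 4). It would be wrong to call that a small loss. The case for age in years rests on a steady gradient being at least as plausible as a step at 75, a value for which the plan gives no reason.

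Three further inferences go too far:

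- **A fixed loss of about 30%.** The figure depends on an age distribution and a linear effect, and the documents state neither.
- **Birth date held for every patient.** It is documented for the UW extract only. At MUSC exact age is a reasonable expectation, since the age criterion has to be checked, but no field list confirms it.
- **Moderation power ignored, or the cut as the main weakness.** Section 8.0 does address moderation power, and no patients are added because the plan regards 264 as enough. Its figure matches a two-group difference and does not cover a .4 SD arm-by-age interaction. That is a larger problem than the cut, and age in years does not cure it.

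**Conclusion.** The point holds as a conditional and inexpensive improvement, not as an error or contradiction in the plan. If the C-CHESS effect changes roughly linearly with age, cutting at 75 loses about 25-44% of the information over the assumed age distributions. A test with power .80 on age in years would then have about .59-.68 with the cut, or .56 at the 44% extreme. For a .4 SD interaction with 264 patients and 35% aged 75 or over, the choice is between about .34 and .47. The age-moderation result will be imprecise under either test and should be reported as such. The importance is minor: it concerns one moderator, and the primary comparison is untouched.

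**What to change.** Before outcomes are examined by arm:

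1. In section 6.0 (Moderation), name arm by age in years (centred) as the age-moderation test for both primary outcomes.
2. Add one simple non-linearity check, for example an arm-by-age-squared term or a restricted cubic spline.
3. Reword the age clause of hypothesis 4 in section 1.0 to match.
4. Report the estimated C-CHESS effect with its confidence interval at chosen ages, for example 70 and 80, and keep the 65-74 versus 75 or over contrast as a supporting display.
5. Confirm that age in years or birth date is in the analysis data for both UW and MUSC.
6. In section 8.0, say that the moderation power statement does not cover a .4 SD arm-by-age interaction.

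The cost is a few lines of wording and one check of data fields, with no added patients or visits. The downside is a true step at 75, where the linear test would lose about 25-44% of the information. Items 2 and 4 are there for that case. The timing matters because a choice between the two tests made after seeing results would not be credible.
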